9.3. Variables

This section outlines patient exposure groups, variable definitions, and study endpoints to be reported across all study objectives. All codes for variable identification will be provided in the statistical analysis plan (SAP). The data source for all variables is Japan MDV.

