			Number of top 5 department visits claims PPPM Note that the top 5 will not be established a priori, but rather will be determined based on the data and sample	HCRU baseline period Follow-up period (overall only)
			Number of top 5 department visits claims PPPD Note that the top 5 will not be established a priori, but rather will be determined based on the data and sample	SUD period

090177e1a4a71ff1\Approved\Approved On: 05-Nov-2025 14:15 (GMT)

Variable	Role	Data Source	Operational Definition	
			Definition	Assessment Period(s)
Degree of nursing	Outcome	MDV	Highest degree of nursing recorded (categorical), N (%) For the following categories: No support, Support level 1, Support level 2, Care level 1, Care level 2, Care level 3, Care level 4, Care level 5, Is applying, Unknown	HCRU baseline period SUD period Follow-up period (overall only)

Abbreviations: ED: emergency department; HCRU: healthcare resource utilization; IP: inpatient; OP: outpatient; PPPD: per patient per day; PPPM: per patient per month; SUD: step-up dosing.

Table 6. Variables for Outcomes (Objective 4 - Other MM treatments including supportive therapy)

Variable	Role	Data Source	Operational Definition	
			Definition	Assessment Period(s)
PIs	Outcome	MDV	Health claim code for bortezomib, carfilzomib, or ixazomib (Yes/No) Health claim code for each PI will also be reported.	Follow-up period
IMiDs	Outcome	MDV	Health claim code for lenalidomide, thalidomide, or pomalidomide (Yes/No) Health claim code for each IMiD will also be reported.	Follow-up period
anti-CD38s	Outcome	MDV	Health claim code for daratumumab, or isatuximab (Yes/No)	Follow-up period

Variable	Role	Data Source	Operational Definition	
			Definition	Assessment Period(s)
			Health claim code for each anti-CD38 will also be reported.	
SCT	Outcome	MDV	Health claim code for SCT (Yes/No) Health claim code for each SCT (allogeneic and autologous) will be reported.	Follow-up period
CAR-T	Outcome	MDV	Health claim code for idecabtagene vicleucel or ciltacabtagene autoleucel (Yes/No) Health claim code for each CAR-T will be reported.	Follow-up period
Chemotherapies	Outcome	MDV	Health claim code for chemotherapies (doxorubicin hydrochloride, melphalan, bendamustine, cyclophosphamide, etoposide, or cisplatin) (Yes/No) Health claim code for each chemotherapy will also be reported.	Follow-up period
IVIG	Outcome	MDV	Health claim code for IVIG (Yes/No)	Follow-up period

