Days from index to first ICANS event	Outcome	MDV	Time in days from index date to first ICANS event (continuous)	CRS/ICANS follow-up assessment period
Cytopenia occurrence ¹	Outcome	MDV	Disease code or labs value for cytopenias occurrences (Yes/No): 
 Anemia Leukopenia Lymphopenia Neutropenia Thrombocytopenia Number and proportion of patients with a health claim code for each cytopenia will also be reported. Incidence and prevalence will be reported, see Section 9.7.2 for additional details.	SUD period
Days from index to first cytopenia	Outcome	MDV	Time in days from index date to first cytopenia (continuous)	SUD period

090177e1a4a71ff1\Approved\Approved On: 05-Nov-2025 14:15 (GMT)

Abbreviations: CRS: cytokine release syndrome; ICANS: Immune effector Cell Associated Neurotoxicity Syndrome; SUD: step-up dosing.

Notes:

1. Variable will be measured as incident and prevalent. Incident cases have a 30-day washout period applied.

Table 8. Variables for Outcomes (Objective 6 - Infections)

Variable	Role	Data Source	Operational Definition	
			Definition	Assessment Period(s)
Infection occurrences ¹	Outcome	MDV	Disease code for infections; the list of infections of interest will be outlined in the SAP (Yes/No) Incidence and prevalence will be reported, see Section 9.7.2 for additional details.	Follow-up period
Days from index to infection	Outcome	MDV	Time in days from index date to first infection (continuous)	Follow-up period
Days between infections	Outcome	MDV	Days between infection claims (continuous) For patients with ≥ 2 disease code for infections listed in the SAP during the time period	Follow-up period

Variable	Role	Data Source	Operational Definition	
			Definition	Assessment Period(s)
Antibiotics	Outcome	MDV	Health claim code for antibiotic treatment (Yes/No)	Follow-up period
Antivirals	Outcome	MDV	Health claim code for antiviral treatment (Yes/No)	Follow-up period
Antifungals	Outcome	MDV	Health claim code for antifungal treatment (Yes/No)	Follow-up period

Notes:

1. Variable will be measured as incident and prevalent. Incident cases have a 60-day washout period applied.

Table 9. Variables for Outcomes (Exploratory Objective 1 – Supportive Medications)

Variable	Role	Data Source	Operational Definition	
			Definition	Assessment Period(s)
Dexamethasone	Outcome	MDV	Health claim code for dexamethasone (Yes/No)	SUD period
Diphenhydramine	Outcome	MDV	Health claim code for diphenhydramine (Yes/No)	SUD period

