9.4. Data Sources

This study will utilize the MDV database. The MDV database is a comprehensive resource containing administrative data from over 540 hospitals in Japan, based on hospital claims data and Diagnosis Procedure Combination (DPC) data. This dataset includes information on demographics; mortality; laboratory tests; inpatient (IP), outpatient (OP), and emergency department (ED) claims; treatments; procedures; and costs of approximately 50 million patients, with a significant proportion of these patients being over 65 years old. The MDV database captures approximately 30% of advanced treatment hospitals in Japan, with over one million health claims processed each month. Additionally, the database includes health claim data from all insurance types (Social, National, and Elderly Insurance), providing a comprehensive characterization of patients and treatment paradigms. The MDV database has been used extensively for use in RW evidence generation (14). Studies have used the MDV database to report on the safety of treatments (15), including the safety of dose schedules (16–18), and treatment patterns in oncology (19–21).

Data is available from April 2008 through the most recent data cut. The MDV database is fully de-identified and aggregated. No individual patient can be identified; therefore, informed consent is not required.

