9.5. Study Size

The study sample will be identified from secondary data from Japanese hospitals that has already been collected. As the MDV database does not include all Japanese hospitals, the sample will be a convenience sample. The most recent data cut available from MDV will be used for the report. All patients who meet the inclusion/exclusion criteria defined in [Section 9.2](#) will be included in the analyses.

This is a descriptive study with no a priori hypotheses; therefore, formal sample size calculations are not applicable. However, to provide an indication of the expected sample size, the February 2025 data cut, MDV included 128 patients that had at least one hospital claim for elranatamab.

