9.7.2. Incidence and prevalence calculations

The incidence of CRS, ICANS, and cytopenias will be determined by counting the number of new cases that arise within a specified time frame, divided by the population at risk during that period. An incident case is defined as a new occurrence of the condition following a 30-day washout period, during which no previous cases are considered. The prevalence of CRS, ICANS, and cytopenia will be calculated by counting the total number of cases (both new and existing) present in the population at a specific point in time, divided by the total population size.

Similarly, the incidence of infections will be calculated by counting the number of new cases that arise within a specified time frame, with a 60-day washout period applied to define new cases. The prevalence of infections will be calculated by counting the total number of infection cases present in the population at a specific point in time, divided by the total population size.

$$\text{Incidence Rate} = \frac{\text{Number of new cases}}{\text{Population at risk}} * \text{Population size}$$

$$\text{Prevalence Rate} = \frac{\text{Number of cases}}{\text{Total population}} * 100$$

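### Table 7 accepts a disease code or a laboratory value for cytopenia occurrence but counts each type of cytopenia by health claim code only

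*Protocol*

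**What the plan says.** The cytopenia row of Table 7 (Protocol, Covariates and Outcomes) opens with the case definition "Disease code or labs value for cytopenias occurrences (Yes/No"), followed by a bulleted list of anemia, leukopenia, lymphopenia, neutropenia and thrombocytopenia. The same cell continues: "Number and proportion of patients with a health claim code for each cytopenia will also be reported". It ends with a pointer: "Incidence and prevalence will be reported, see Section 9.7.2 for additional details".

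Section 9.7.2 describes the numerator in general terms: "The incidence of CRS, ICANS, and cytopenias will be determined by counting the number of new cases that arise within a specified time frame". It does not say whether a cytopenia case is identified by code, by laboratory value or by either, or whether the results are given by type.

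Section 9.4 lists the contents of the database as separate items, among them "laboratory tests; inpatient (IP), outpatient (OP), and emergency department (ED) claims". Section 9.3 leaves the code lists to the SAP: "All codes for variable identification will be provided in the statistical analysis plan (SAP").

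**The concern.** One table cell holds two case definitions for the same events. If the second sentence is the breakdown of the first, a patient with neutropenia seen only in the laboratory data has a cytopenia under the occurrence variable but is not counted under neutropenia. If none of that patient's cytopenias is coded, the patient appears under no type at all. The overall figure and the type figures would then stand in one table on different bases, with nothing to tell the reader so.

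The type counts carry the specific information, because an overall figure does not separate neutropenia from anemia. Cytopenias are named in secondary Objective 5 of a study designated as a post-authorization safety study. Section 9.9 already expects safety events to be underestimated in these data. Leaving laboratory evidence out of the type counts would add an under-count that the study's own variables can avoid.

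**Working it through.** The protocol states no cytopenia rate, so there is no figure to reproduce. The check is a comparison of texts followed by set inclusion.

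**1. The two definitions.**

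| Item in the cytopenia row | Evidence accepted |
|---|---|
| Occurrence (Yes/No), five types listed | disease code or laboratory value |
| Number and proportion for each type | health claim code |
| Incidence and prevalence | not stated; refers to Section 9.7.2 |

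**2. Could a health claim code include a laboratory value?** Section 9.4 names laboratory tests apart from inpatient, outpatient and emergency claims. A claim for a test would show that it was done, not what it found. Nothing in the protocol puts laboratory results under claim codes.

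**3. Is the second sentence the breakdown?** The drug rows in Tables 3 and 6 give a composite Yes/No and then its components. For proteasome inhibitors the second sentence is "Health claim code for each PI will also be reported". There both levels use claim codes, so nothing is lost. The cytopenia row follows the same pattern, but its first level also admits laboratory values. The next row of Table 7, time from index to the first cytopenia, also treats cytopenia as a single outcome. Both points favour reading the sentence as the component breakdown.

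**4. The consequence.** For a given type, let C be the patients with a code and L the patients with a qualifying laboratory value. Assume that the claim code for a cytopenia is the same thing as its disease code. Then

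n(C or L) = n(C) + n(L without C),

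so n(C) = n(C or L) − n(L without C) ≤ n(C or L).

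The two counts are equal only if no patient has that type by laboratory value alone. One such patient is enough to make the code-only count smaller.

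**5. Size.** The shortfall as a proportion of the cohort is p × f, where p is the code-or-lab proportion for that type and f is the share of those patients found by laboratory value alone. The protocol gives neither. Its only related figure is the indicative cohort in Section 9.5 ("MDV included 128 patients that had at least one hospital claim for elranatamab"), which fixes neither p nor f. The direction follows from step 4; the amount cannot be derived.

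**The case against.** The strongest reply is that the layout permits a milder reading. The code-or-lab definition ends in a colon and the five types follow as bullets, so each type may itself be flagged by code or laboratory value. The word also in the next sentence would then announce an additional claim-code tabulation. The drug rows differ in form: they join the drug names with or before the Yes/No, which makes the composite explicit, whereas the cytopenia row never names an any-cytopenia total. On this reading no laboratory-only case is lost. This stands as a possible reading, and it is why the point is conditional on the literal one. The row does not state it, however, and a reader of the results could not tell which count is shown.

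A second reply is that terms are used loosely across these tables (Table 7 refers to a disease code for concomitant medications), that codes are deferred to the SAP, and that Section 9.7 lets the SAP modify the plan. It is fair to see a wording slip here, perhaps carried over from the drug rows, rather than a deliberate choice. But a code list does not add a laboratory criterion to a count defined by claim code, and Section 9.8 says the protocol will be strictly followed.

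A reader might also infer that the incidence and prevalence figures are code-only. The documents do not support that: those measures attach to the occurrence variable, which opens with the code-or-lab definition, and Section 9.7.2 imposes no claim-code restriction. Section 9.7.2 simply leaves the definition unstated.

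**Conclusion.** The point holds in a limited form. As worded, the type-specific cytopenia counts rest on a claim code alone while the occurrence variable also accepts laboratory values. The more natural reading makes the type counts narrower than the variable they break down. They cannot exceed the code-or-lab counts and they miss every laboratory-only case. This rests on two assumptions: that the sentence is the component breakdown, and that claim code and disease code mean the same thing for a cytopenia.

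The size is unknown and may be zero. It is tempting to infer a large understatement by assuming what fraction of laboratory-evident cases is coded. The documents give no such fraction, and that fraction alone would not settle the ratio, because cases coded without a qualifying laboratory value also enter the code-or-lab count. A reader might further infer that the 30-day washout has to be applied within each type; that is a separate question which this wording does not establish.

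The affected output is a descriptive result of a secondary objective. No primary objective or formal comparison depends on it. The correction is still worth making because it is nearly free and removes an ambiguity from a safety table.

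**What to change.** In the Table 7 cytopenia row, replace health claim code with disease code or lab value in the sentence on each cytopenia, so that the types and the occurrence variable share one definition. If a claim-code-only count is wanted, give it its own column and label it as such. Add to Section 9.7.2 that cytopenia cases for incidence and prevalence are identified by disease code or laboratory value.

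The cost is one changed sentence in Table 7 and a short addition to Section 9.7.2. The laboratory criteria already have to be specified and programmed for the occurrence variable, so little extra programming is needed and no further data.

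### Table 7's time to first cytopenia is not limited to incident cases, so a cytopenia that predates elranatamab and is recorded again can count as early onset

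*Protocol*

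**What the plan says.** Protocol, Table 7 (Objective 5), has two cytopenia rows, both assessed over the SUD period.

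- The occurrence row counts a case as "Disease code or labs value for cytopenias occurrences (Yes/No"), covering anemia, leukopenia, lymphopenia, neutropenia and thrombocytopenia. It carries the footnote marker: "Cytopenia occurrence ¹". The footnote reads "Variable will be measured as incident and prevalent. Incident cases have a 30-day washout period applied".
- The timing row reads "Time in days from index date to first cytopenia (continuous"). It has no footnote marker and does not say whether it uses incident cases or all cases.

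Section 9.7.2 uses the washout in the same limited way. For incidence, "An incident case is defined as a new occurrence of the condition following a 30-day washout period". Prevalence is obtained by "counting the total number of cases (both new and existing) present in the population at a specific point in time".

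Section 9.2 starts the SUD period at the first 44 mg vial and makes it inclusive. For a patient who begins with that vial, the index date is therefore inside the window. Table 2 has the cytopenia outcomes reported for Groups A, A+B and C, and Section 9.7.5 repeats Objective 5 in the low-weight subgroup.

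Table 8 (Objective 6) words its infection timing row in the same way, "Time in days from index date to first infection (continuous"). Its 60-day washout is likewise footnoted only on the occurrence row.

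**The concern.** A reader will take a time from index to first cytopenia as a description of when cytopenia begins after elranatamab is started. That reading needs patients who were free of the cytopenia at time zero. The protocol recognises this for incidence and imposes a washout, but it does not carry the condition to the timing row.

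The approved indication, as Section 7 gives it, is relapsed or refractory disease after exposure to three drug classes, so low counts before the first dose are plausible. The SUD window is short, so a few records on day 0 or soon after can move the summary a good deal. Because the five types are pooled, one old cytopenia uses up the patient's first event.

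Nothing else in the protocol would show a reader how much of this has happened. Table 3 lists none of the five cytopenias as a baseline characteristic, and Section 9.7.6 plans no sensitivity analysis.

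**Working it through.** The protocol states no expected onset time, event count or baseline cytopenia rate, so there is no figure to reproduce. The check has two parts.

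**1. Following one patient through the definitions.** Suppose a patient was anemic in the month before index, has a low hemoglobin recorded on the index date, and becomes newly neutropenic on a later day d within the SUD period.

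- Incidence (Section 9.7.2): the anemia fails the 30-day washout and is not a new case. The neutropenia is new on day d, provided the washout is applied by type.
- Prevalence: both are counted.
- Timing row, read literally: the first qualifying record in the window is the hemoglobin, so the value is 0 days and day d is never used.

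The same patient is an incident case on day d in one line of the table and an onset at day 0 in another. A prior cytopenia enters the timing row only if it is coded or measured again within the window.

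**2. Illustrating the direction.** All of these inputs are assumptions, not protocol figures:

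- p = share of patients with a cytopenia already present and recorded on day 0, from 0.2 to 0.8
- i = share of the remaining patients who develop a new one in the window, from 0.3 to 0.7
- new cases spread evenly over days 1 to L, with L = 7 or 14. Group A allows two intervals of 1 to 7 days, so its window runs from 2 to 14 days.

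Formulas:

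- Share of first-cytopenia times that are pre-existing: s = p / (p + (1 − p) i)
- Mean as written: (1 − s)(L + 1)/2
- Mean among new cases only: (L + 1)/2, which is 4.0 days for L = 7 and 7.5 days for L = 14
- The median is 0 when s exceeds 0.5, that is, when p exceeds i/(1 + i)

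For p = 0.4 and i = 0.5: s = 0.4/(0.4 + 0.6 × 0.5) = 0.57. The mean is 0.43 × 4.0 = 1.7 days for L = 7 and 0.43 × 7.5 = 3.2 days for L = 14.

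| p | i | s | Mean, L = 7 | Mean, L = 14 | Median, L = 7 / L = 14 |
|---|---|---|---|---|---|
| 0.2 | 0.7 | 0.26 | 2.9 | 5.5 | 3 / 5 |
| 0.2 | 0.3 | 0.45 | 2.2 | 4.1 | 1 / 2 |
| 0.4 | 0.5 | 0.57 | 1.7 | 3.2 | 0 / 0 |
| 0.6 | 0.5 | 0.75 | 1.0 | 1.9 | 0 / 0 |
| 0.8 | 0.3 | 0.93 | 0.3 | 0.5 | 0 / 0 |

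The median reaches 0 once p exceeds 0.3/1.3 = 0.23, 0.5/1.5 = 0.33 or 0.7/1.7 = 0.41, for i = 0.3, 0.5 or 0.7. Every case shortens the time. How far depends wholly on p, i and the assumed timing.

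**The case against.** The strongest reply is that the timing row is silent rather than wrong. It does not say that existing cases count, the row above is measured both as incident and as prevalent, and the SAP could tie timing to incident cases. This stands in part: the text does not prove what will be programmed. But Section 9.3 presents these tables as the variable definitions and leaves the codes to the SAP, and Section 9.8 says the protocol will be strictly followed. Applied literally, the row takes the first qualifying record, and no other section narrows it.

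A second reply is that Objective 5 concerns incidence and prevalence, that both are reported, and that no formal group comparison is planned. This also stands in part. Cytopenia incidence has its washout and is unaffected, and setting it beside prevalence gives some view of carry-over. The affected item is one supplementary descriptor under a secondary objective. It should still describe what its label suggests.

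A reader might go further in four ways that the documents do not support:

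- That the variable merely records when blood was first tested. Disease codes also qualify, so this is too absolute.
- That the bias has a known size. No baseline rate is given.
- That the infection row is equally affected. Table 8 infections need a disease code, with no laboratory route, and are followed over the whole follow-up period, so routine testing on day 0 matters less.
- That every index-date blood count must have preceded the injection and belongs to baseline. The protocol does not say whether the time of day is recorded, and a blanket rule would misclassify any true same-day onset.

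**Conclusion.** The point holds as a badly fixed definition. The timing row lacks the restriction that the protocol applies to incidence, its window opens on the first-dose day, and it pools five cytopenias. A pre-existing cytopenia that is recorded again can therefore be shown as early onset and can mask a later new one. Onset time and incidence then describe different sets of cases.

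The direction is toward shorter times. The size cannot be stated from the protocol. The illustrated falls, from 4.0 to 0.3–2.9 days and from 7.5 to 0.5–5.5 days, rest on assumed shares, even timing of new cases and all carry-over falling on day 0. If carried-over cases were recorded later in the window, or not at all, the effect would be smaller.

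The conclusion for infections is one of consistency only.

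**What to change.** In Table 7, define the timing variable as days from index to the first incident cytopenia. Apply the stated 30-day washout before index separately to each of the five types, with a case excluded for a given type if a code or qualifying laboratory value for that type falls in those 30 days. Report the number and percentage of patients with each cytopenia already present at index as a separate line.

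In Table 8, tie the infection timing row to incident cases under its 60-day washout.

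How to treat laboratory values dated on the index date is an optional choice and not part of this correction.

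The cost is a change of wording in two tables, minor programming and fewer contributing patients. Applying the illustration to the 128 patients in the February 2025 cut, p = 0.4 and i = 0.5 would leave 128 × 0.3 ≈ 38 contributors instead of 128 × 0.7 ≈ 90. That is before eligibility and the split into SUD groups. It overstates the loss, because a patient with one old cytopenia could still contribute a new one of another type.
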